Randomization Procedures, Preparation, and Allocation of Study Bottles. IDS consultants will randomize and prepare the study probiotic and placebo capsules, independent of [name] and other study personnel. A simple randomization computer program will be used by the IDS consultants to generate the random number sequence used to randomly assign study participant numbers to receive either the probiotic or placebo capsules. The IDS staff will fill 58 bottles (each containing 112 probiotic pills) and 58 bottles (each containing 112 placebo pills) and label them in a manner that is blind to group assignment, indicating study numbers assigned from 1-116. The original list identifying the allocation and relationship to study number will be kept locked in the IDS, unavailable to [name] or other study personnel until study completion, when unblinding will occur. Each study bottle will be covered with a MEMS cap (electronic cap counter) and placed in the refrigerator in the Aurora Sinai Medical Center Inpatient Pharmacy (ASMCIP). When the SC enrolls participants, retrieval of the prepared study bottles from the ASMCIP will occur with distribution of the specific participant's bottle that corresponds to the assigned study number.

Intervention Initiation and Duration. The **rationale** for third trimester (28 ± 2 weeks gestation) initiation of the probiotic intervention is based on the findings of our review of the scientific literature on antenatal probiotics. In 23 of the 31 RCTs included in our integrative review, the intervention was initiated in the third trimester without any adverse maternal, fetal, or neonatal outcomes. The intervention will be continued until labor to maintain microbiota effects (probiotic group) at the critical time for newborns. All participants will be instructed to keep the study bottle refrigerated and to take one capsule per day until they are in labor. We found no rationale to recommend "catch up" dosing if participants miss a capsule. Participants will return study bottles with any remaining unused capsules to SC at 1-2 days post birth.

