Adherence. Adherence⁵⁸ will be measured in three ways: (a) A MEMS™ AARDEX™ electronic cap counter⁵⁹ will be placed on each numbered study bottle. Each opening of the bottle cap is recorded by an electronic chip that is linked to the SC's computer. (b) When bottles are returned during the post birth hospital stay, the remaining capsules will be counted to verify the MEMS cap count. (c) The qualitative 16S rRNA targeted sequencing method and PCR performed on vaginal and rectal swabs will recover probiotic bacteria contained in Florajen3. Two approaches designed to encourage participants' daily adherence are: (a) Each participant will receive a daily text message reminder⁶⁰ to take her study capsule. The participant will choose the timing of the daily text message. If the participant cannot receive text messages, she will be offered a refrigerator alarm. ^{61,62} (b) At prenatal and study visits participants will be reminded to take capsules daily.

Procedure and Timing. Table 2 contains a summary of data collection, variables, measures, and timing. Following IC, the SC will sequentially distribute the prelabeled, randomly numbered bottles of study capsules, as noted above. The SC will maintain a list of the participant names, linking them to the assigned study

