numbers, in an encrypted computer file, accessible only to the PI and the SC. The PI, co-investigators, SC, prenatal providers, and participants will be blind to group assignment. Data will be collected at five time points: T1 baseline (28 ± 2 weeks), T2 (36 ± 2 weeks), T3 (1-2 days post birth, before hospital discharge), T4 (2 weeks post birth phone call), and T5 (2 months post birth follow-up phone call). Measures and documentation tools appear in Appendices A through G. At each study visit, participants will be asked about any potential adverse events. Immediately following IC, participants will have their first study visit at 28 ± 2 weeks gestation (T1), during which baseline data will be collected and they will receive instructions to take one capsule by mouth daily until the time of birth. Also at T1 (28 ± 2 weeks), the participant will be seen by her prenatal provider, who will facilitate collection of the baseline study samples. Participants will be asked to collect their own vaginal and rectal swabs with assistance, but have the option of provider collection. This minimally invasive testing does not require a speculum exam. Self-collected swabs yield similar colonization measures compared to provider-collected, but may be more acceptable to women. 63,64 Each participant will also complete three brief questionnaires at T1. Vaginal and rectal swabs and 2 questionnaires will be collected at T2 (36 ± 2 weeks). At the end of T2, participants will receive a \$25 gift card. At T3, the SC will visit every participant on the postpartum hospital unit to administer two brief questionnaires, retrieve the study bottle with MEMS cap, and give a \$75 gift card. The SC will analyze the MEMS cap data, count and record the capsules remaining in the bottle, and conduct a chart review. At T4 and T5, the SC will text message the participants to indicate that she/he will be phoning the next business day. The following day, a phone call will be made to the participant to elicit any maternal and child health events (e.g., illness, antibiotics, or hospital readmission). At T5, the SC will also retrieve health records for the participant and her infant to examine them for the same maternal or child health events.

Table 2. Summary of Study Data Collection, Variables, Measures, and Timing

Outcome Variables	Study Data Collection	T1	T2	T3	T4	T5
	SC will document data from all measures on the Summary	28 ± 2	36 ± 2	1-2 days	2	2

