 - c. Quantitative Lactobacillus Colony Counts. The swabs of vaginal and rectal sites will be analyzed to

identify the actual number of Lactobacilli in each area, counted as CFUs per swab (T1 &T2).

- d. Intervention Adherence Measures
- d.1. **PCR** and **16s** rRNA **Targeted Sequencing**. Vaginal and rectal swabs for PCR and 16s rRNA targeted sequencing will be collected (T2) by the participant or her provider and sent to [name] lab for analysis to detect the presence of the probiotic strains contained in the probiotic intervention group, verifying adherence.
- d.2. **MEMS Caps.** Each opening of the MEMS[™] AARDEX[™] wireless electronic cap counters^{58,59} will be recorded electronically with a software link to a study computer accessible to the SC and [name].
 - d.3. **Pill Counts.** The MEMS cap counts will be verified by the pill count when the bottle is returned.
- e. **Maternal GI Symptoms.** Because currently available GI quality of life scales focus on specific pathologies, we adapted the previously validated 7-item, non-pain symptom scale of the Severity of Dyspepsia Assessment (SODA)⁶⁵ (Cronbach's α = 0.9) to operationalize this variable. For use during pregnancy, the symptoms of "diarrhea" and "constipation" were added, resulting in a 9-item scale. Participants rate the severity of each symptom over the past week on a 6-point Likert scale, ranging from 0 = *no problem, not present* to 5 = *very severe problem, markedly influences daily activities and/or requires rest.* The score on the 9 items is summed to arrive at a GI symptom score ranging 0-45. Our **Ante-Partum Gastrointestinal Symptom Inventory (AP-GI-SA)** was validated in a pilot study with a sample of 45 healthy pregnant women. ⁶⁶ We found Cronbach's α = 0.84, test-retest reliability, stability, and content and face validity (T1, T2, and T3).
- f. IAP. If GBS-positive, the number and type of IAP doses will be recorded by SC on the **Summary Data Collection Form (SDCF).** Additional prenatal and intrapartum antibiotic exposures for participants and infants will be recorded on this form by the SC as potential cofounding variables.
 - g. Potentially cofounding variables
 - g.1. Participants will complete the brief **Demographic Questionnaire (DQ)** at T1 only.

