- g.2. Participants will complete the **Questionnaire for Women (Q4W)** at T1-T3 visits. To improve the reliability of subject recall, the Q4W asks for a report of the past week's ingestion of yogurt, vaginal cleansing practices, and sexual activity. The Q4W was used by the co-investigators in our preliminary study.¹⁸
- h. **Maternal-Infant Postpartum Health Events.** The SC will interview the participant for a history of postpartum health events for herself or the infant (T4 and T5) and document appropriately on two forms:
 - h.1. Maternal health events, recorded on Maternal Peripartal Health Check (MPHC).
 - h.2. Infant health events, recorded on Infant Health and Wellness Form (IHWF).
- i. **Adverse Events.** All providers and study personnel will solicit information about potential adverse events (AE) at each study visit (T2 through T5). Participants will be asked to report any suspected side effects or AE at any point in between study visits to their providers, who will then notify the PI, and follow the protocol established in the Human Subjects Section. AE will be recorded on **Q4W** (T2, T3), **MPHC and IHWF** (T4-T5). **Data Management.** Database and entry screens for this project will be developed using Epidata. To minimize errors, data will be double-entered and checked for invalid codes, values that are out of range, invalid dates, and skip patterns. All data will be verified against the original forms and imported to Epidata for analysis. **Descriptive Analyses.** Means, standard deviations or frequency distributions will be reported for all variables. We will test for differences in demographic characteristics of two groups (Florajen3 and placebo), including confounding variables such as sexual activity, vaginal hygiene practices, yogurt ingestion, and prenatal antibiotic use. Chi-square and independent *t* tests will be used to compare mode of birth, gestational age at birth, and birth weight and length, to assess equivalence of groups. Chi-square, Fischer's exact tests, and Wilcoxon methods will be used to test for difference among binary and categorical variables.

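### No adverse event question is scheduled between the first capsule (T1) and T2, 4 to 12 weeks later, and the look-back period for the T2 and T3 questions is not stated

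*Combined protocol and SAP*

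**What the plan says.** **Exposure.** The visit windows under Procedure and Timing are "T1 baseline (28 ± 2 weeks), T2 (36 ± 2 weeks"). Capsules are given out at T1, where "they will receive instructions to take one capsule by mouth daily until the time of birth".

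**Scheduled AE questions.** Item i (Adverse Events) reads "All providers and study personnel will solicit information about potential adverse events (AE) at each study visit (T2 through T5"). The AE row of Table 2 agrees: blank at T1, marked from T2 to T5. Procedure and Timing is broader: "At each study visit, participants will be asked about any potential adverse events", with no exception for T1.

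**Between visits.** Item i also tells women to report anything they suspect to be a side effect or AE to their providers whenever it arises. Providers then notify the principal investigator and follow a procedure in a Human Subjects Section, which is not among the documents available here.

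**Forms.** Item i places AEs on the Questionnaire for Women (Q4W) at T2 and T3, and on the maternal (MPHC) and infant (IHWF) health forms at T4 and T5. Item g.2 says "the Q4W asks for a report of the past week", and the same sentence ties that window to yogurt, vaginal cleansing and sexual activity. For the GI scale, item e says "Participants rate the severity of each symptom over the past week".

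**Existing contacts.** Under Adherence, "At prenatal and study visits participants will be reminded to take capsules daily", and each woman receives a daily text reminder at a time she chooses (a refrigerator alarm is offered if she cannot receive texts).

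**The concern.** Item i and Table 2 give no scheduled AE contact in the first weeks on product. What is learned about those weeks depends on a woman recognizing a problem as possibly related and reporting it unprompted, or on her remembering it at T2. Three kinds of event are exposed to loss: those that begin and resolve before T2, those that lead a woman to stop capsules, and those in women who leave the study before T2. A woman in the last group may never be asked a scheduled AE question while on product.

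The plan has clinic visits and a messaging system running through this interval, but describes them only as adherence reminders. A tolerability summary by arm would therefore rest on unprompted reports for the early period and on scheduled questions later, with nothing in the plan to tell the reader how far back the later questions reach.

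**Working it through.** The plan states no figure of its own on this point, so there is none to reproduce. The check is arithmetic on the visit windows, followed by a comparison of the sections.

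**1. Gap from first capsule to first scheduled on-treatment AE question**

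Inputs (Procedure and Timing): T1 = 28 ± 2, so 26 to 30 weeks; T2 = 36 ± 2, so 34 to 38 weeks.

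- Shortest: 34 − 30 = 4 weeks
- Longest: 38 − 26 = 12 weeks
- Nominal: 36 − 28 = 8 weeks

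The broader sentence in Procedure and Timing does not change this. Capsules are first dispensed at T1, so an AE question there gives a baseline only.

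**2. Share of exposure before that question**

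Formula: (T2 − T1) / (labor − T1). The documents give no expected gestation at labor; 37, 39, 40 and 42 weeks are assumptions.

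| T1 | T2 | Labor (assumed) | Share before T2 |
|---|---|---|---|
| 28 | 36 | 40 | 8/12 = 67% |
| 30 | 34 | 42 | 4/12 = 33% (lowest) |
| 26 | 38 | 39 | 12/13 = 92% (highest) |

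The range covers combinations in which T2 comes before labor. The interval is usually, but not always, the larger part of exposure. As a cross-check, each bottle is described as "each containing 112 probiotic pills", with the same number of placebo capsules in the other arm; 112/7 = 16 weeks of supply, equal to the longest exposure considered (42 − 26 = 16).

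**3. What the T2 and T3 questions look back over**

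- Item i names the Q4W as the recording form and states no look-back for AEs.
- Item g.2 gives the Q4W a past-week window for three behaviors only.
- Item e gives the GI scale a past-week window; that scale is an efficacy outcome (hypothesis 2).

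The AE question could reach back to T1 or cover only the past week; the documents do not settle which. No percentage of exposure covered follows from them.

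**4. Infant events at T3**

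| Place | T3 | T4 and T5 |
|---|---|---|
| Table 2, maternal-infant health row | marked; interview on maternal and infant events and potential AEs | marked |
| Item h (interview; MPHC, IHWF) | not listed | listed |
| Item i (AE forms) | Q4W | MPHC, IHWF |

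Table 2 schedules the T3 interview. Items h and i name no infant form for it.

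**The case against.** The strongest case on the other side is that early events are not left uncaptured. Women are instructed to report between visits, providers must pass reports on, and the governing procedure sits in a section that was not available here. The data forms are in appendices that were not available either, and may already word the AE question to cover the whole interval. MEMS caps record every bottle opening, so the timing of stopping can be seen. The coordinator visits every participant at T3 and reviews the chart; calls follow at T4 and T5, and T5 adds health records. The protocol also cites third-trimester initiation in 23 of 31 reviewed trials without adverse outcomes.

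Much of this stands, and it rules out two stronger readings that a reader might infer.

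- **That most of the exposure period has no structured safety capture.** This would require applying the one-week window to AEs, giving for example 2 of 12 weeks (17%) from T2 and T3 together. The documents attach that window to three behaviors and to the GI scale, not to AEs.
- **That early intolerance explains dropout in the preliminary study.** Sample Size and Power Estimates gives 23% overall and 30% on probiotic, with neither reasons nor timing.

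What the objection does not remove is the absence of any scheduled AE question between T1 and T2. Instructed self-report depends on the woman suspecting an event. MEMS data show when capsules stopped, not why. T3 and later contacts come after exposure has ended. The T3 form mismatch is close to clerical, but still needs correcting.

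**Conclusion.** The point holds in a limited form. Item i and Table 2 place the first scheduled on-treatment AE question 4 to 12 weeks after the first capsule, nominally 8. At the nominal visit weeks that is 67% of exposure if labor is at 40 weeks, and 33% to 92% across the visit windows with labor assumed at 37 to 42 weeks. Over that interval AE capture rests on participant-initiated reports and on recall at T2, with the look-back unstated.

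This supports a specific, inexpensive improvement to safety capture. It does not show that early events would go unrecorded, and it supports neither a coverage percentage nor a link to the earlier dropout. The conclusion assumes that the Human Subjects Section and the appendix forms, which were not available, add no scheduled AE contact before T2. If they do, what remains is to align item i and Table 2 with them and to settle the T3 form.

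**What to change.** In item i and the AE row of Table 2:

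1. Have providers or the coordinator ask about AEs at the routine prenatal visits between T1 and T2, or add a periodic AE prompt to the daily text. Record onset date, stop date and whether capsules were stopped. Women using the refrigerator alarm instead of texts would need the prenatal-visit route.
2. Word the T2 and T3 AE question as 'since your last study contact', and keep it apart from the Q4W's past-week items.
3. Reconcile the T3 entries: Table 2 schedules maternal-infant events and potential AEs at T3, item h lists only T4 and T5, and item i puts T3 AEs on the Q4W. Name the form that holds infant events at T3; extending the MPHC and IHWF to that visit would do this.
4. Align Procedure and Timing with item i on whether T1 is included and, if so, label it as baseline.

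The cost is form wording, one added question at visits already taking place or a prompt on an existing system, and edits to Table 2 and items h and i. No new visits are needed. The downside is more minor AEs to log.

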Sample Size and Power Estimates. A provider group within the proposed study setting reported a 29.4% prevalence of GBS positive women among the 316 who gave birth in 2016. Therefore, we expect a 30% GBS prevalence in the placebo group compared to the probiotic group. To determine the effect size of the intervention, a sample of 80 women will be required to test the difference in proportions of GBS colonization and IAP between groups (hypotheses 1a and 1d). Hypotheses are unidirectional. With the sample size of 80 and setting alpha = 5%, one tailed test, 80% power estimate, and confounding variables (yogurt ingestion, vaginal cleansing practices, and sexual activity) accounting for multiple R-square = 0.1, we will be able to reject the null hypothesis for an effect size of Odds Ratio (OR) = 0.17 for the logistic regression to compare the proportion of GBS positives between groups. When comparing the colony counts (GBS and Lactobacillus) and GI symptoms (hypotheses 1b, 1c and 2), the same sample size = 80, power = 80%, alpha = 5%, one tailed test; we can reject the null hypothesis for a Cohen d = 0.56. This is a medium effect size, indicating that we can detect a difference between groups equivalent to 0.56 standard deviations. However, if the effect of the treatment is smaller we will be able to identify it, but not reject the null hypothesis of being equal to 0. This information is important for design of a full scale efficacy trial of the probiotic intervention. In our published preliminary study, 15 we found an overall dropout rate of 23%, but 30% in the probiotic group. For the proposed study, we chose a conservative 30% dropout rate to assure that the sample size can be fully achieved within the study timeline. Therefore, a total sample of 116 will be targeted for enrollment. Hypotheses 1b, 1c, and 2 will be tested by doing a multiple group comparison of the change in colony count for GBS and Lactobacillus, and the GI symptom inventory (M-SODA-9) scores [Section 2.3.1.8.e].

Recruitment. A sample of 116 women who meet the inclusion criteria, low-risk, healthy and pregnant, 26 ± 2 weeks gestation, 18 years of age, will be recruited from a population of central city maternity care recipients who see either certified nurse-midwives or physicians at the prenatal clinics of Aurora Sinai Medical Center (ASMC) in Milwaukee, Wisconsin. Approximately 200 new prenatal patients are seen monthly. **Inclusion and exclusion criteria are detailed in Table 1.**

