All participants regardless of group assignment will receive usual prenatal care. To facilitate recruitment, posters will be displayed in the waiting areas and in each prenatal examination room, and recruitment brochures will be available. The Study Coordinator (SC) will work with the clinic receptionist staff to identify women at 26 ± 2 weeks gestation on the day of their visit to the clinic. Participants will begin the study at 28 ± 2 weeks gestation. Once identified and introduced to the study by the SC, potential participants will be provided with a copy of the informed consent document. If she expresses an interest in the study, she will provide her name, due date, birth date, and phone number, as well as permission to be screened for study participation. The SC will conduct a prenatal chart review for study inclusion and exclusion criteria for each interested woman by completing the Prenatal Eligibility Screening Form (PESF)The SC will call the woman, thank her for her interest, and indicate whether she meets the study eligibility criteria. For those eligible and willing, the SC will arrange to meet the potential participant in the clinic just before her regularly scheduled prenatal visit at 28 ± 2 weeks gestation. Upon meeting, the SC will explain the study, review the informed consent (IC) document, and answer all questions, to complete IC procedures. The same setting and recruitment procedures were used for the team's preliminary study. 18 During the IC, participants will be apprised that they will begin taking oral study capsules once daily from 28 ± 2 weeks until labor. Participation is completed at 2 months postbirth. Intervention. Floraien3 is a combination probiotic with a once daily recommended dose. Each commercial batch of Florajen3 undergoes rigorous testing for potency, purity, and dose. Potency is maintained for 14 months when refrigerated. Subjects in the control group will take a daily placebo capsule of rice maltodextrin, identical in appearance, taste, and smell to the probiotic capsules. American Lifeline will ship the bulk probiotic and placebo products to the Aurora Investigational Drug Service (IDS) for the study.

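### Birth outcomes measured after treatment are tested for difference in order to assess whether the groups are equivalent, which such tests cannot show

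*Combined protocol and SAP*

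**What the plan says.** Descriptive Analyses first provides for testing demographic characteristics and named confounders between the Florajen3 and placebo groups. The next sentence adds chi-square and independent t tests "to compare mode of birth, gestational age at birth, and birth weight and length, to assess equivalence of groups". The paragraph closes by saying that chi-square, exact and Wilcoxon methods "will be used to test for difference among binary and categorical variables". Every test named there is a test of difference. No equivalence margin, confidence interval or equivalence procedure is given for the birth variables here or elsewhere in the document.

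On timing, the Recruitment section says participants are told that "they will begin taking oral study capsules once daily from 28 ± 2 weeks until labor". Intervention Initiation and Duration, and Procedure and Timing, agree with this.

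Sample Size and Power Estimates covers only GBS colonization, antibiotic prophylaxis (IAP), colony counts and GI symptoms. For the continuous outcomes among these it states "we can reject the null hypothesis for a Cohen d = 0.56", and it adds that "if the effect of the treatment is smaller we will be able to identify it, but not reject the null hypothesis".

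**The concern.** Two things go wrong in one clause.

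First, delivery route, gestational age, weight and length at birth all come after randomization and after exposure to study product. A difference between arms could be chance or an effect of treatment. Similarity or difference on these variables says nothing about whether randomization produced comparable groups.

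Second, if equivalence is meant literally, a p-value above 0.05 from a difference test is not evidence for it. In a trial of this size such a result is likely even when a moderate true difference exists. The sample size section itself accepts that smaller effects will not lead to rejection of the null, so non-rejection cannot then count as support for equivalence.

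At stake is how the birth results are read. Four non-significant p-values could be reported as showing the arms equivalent when the data leave sizeable differences open.

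**Working it through.** **Inputs from the document.** Analysable sample: "a sample of 80 women will be required to test the difference in proportions of GBS colonization and IAP between groups". Error rates for the study hypotheses: "setting alpha = 5%, one tailed test, 80% power estimate". Attrition: "we chose a conservative 30% dropout rate". Enrolment is 116, with 58 bottles prepared per arm, so allocation is taken as 1:1.

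**Assumptions.** The plan gives no alpha or sidedness for the birth-variable tests, so two-sided 5% is used. Women per arm (n) run from 40 (80/2) to 58 (116/2, no loss), because the document does not settle how many women will have birth data. Results for continuous variables are in SD units, since no SDs are given.

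**1. The plan's own figures.** n per arm = 2(1.645 + 0.842)²/0.56² = 39.4, rounded up to 40, or 80 in total. The exact one-sided t test at 40 per arm has power 0.799 for d = 0.56. For dropout, 40/0.7 = 57.1, rounded up to 58 per arm, or 116. Both stated figures reproduce.

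**2. Precision of a mean difference.** The 95% half-width in SD units is t(0.975, 2n − 2) × √(2/n).
- n = 40: 1.991 × 0.2236 = 0.445
- n = 58: 1.981 × 0.1857 = 0.368

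Even an observed difference of zero leaves true differences of that size inside the interval. In the extreme case, where the observed difference falls just short of significance, the interval reaches about twice as far: 2 × 0.445 = 0.89 SD, or 2 × 0.368 = 0.74 SD.

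**3. Chance of missing a true difference.** This is one minus the two-sided noncentral-t power, with noncentrality d√(n/2).

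| True difference | Power, n = 40 | Missed | Power, n = 58 | Missed |
|---|---|---|---|---|
| 0.3 SD | 0.263 | 74% | 0.360 | 64% |
| 0.4 SD | 0.424 | 58% | 0.570 | 43% |
| 0.5 SD | 0.598 | 40% | 0.761 | 24% |

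The difference detectable with 80% power is 0.63 SD at n = 40 and 0.52 SD at n = 58.

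**4. Mode of birth.** The document gives no cesarean rate, so 15% to 35% is assumed. The half-width is 1.96 × √(2p(1 − p)/n): 16 to 21 percentage points at n = 40, and 13 to 17 at n = 58. Power for a 10-point increase is Φ[(0.10 − 1.96·SE₀)/SE₁], with SE₀ from the pooled proportion and SE₁ from the separate proportions. It is 0.198 to 0.146 at n = 40, so 80% to 85% are missed. At n = 58 it is 0.268 to 0.193, so 73% to 81% are missed.

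**5. What a formal equivalence test would offer.** Take two one-sided 5% tests with margin m and a true difference of zero. By normal approximation, power is 2Φ(m/√(2/n) − 1.645) − 1, set to zero where that is negative.
- m = 0.5 SD: 2.236 − 1.645 = 0.591 at n = 40, power about 0.45; 2.693 − 1.645 = 1.048 at n = 58, power about 0.70
- m = 0.3 SD: about zero at both sizes

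For 80% power, n = 2[(1.645 + 1.282)/m]², giving 69 per arm for 0.5 SD and 191 for 0.3 SD. The planned size could support only wide margins.

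**The case against.** The best defence is that this is loose wording in a descriptive section. Hypotheses 1a-1d and 2 are analysed by the generalized linear model, the mixed model and the factor analysis described in later sections. No decision or model choice depends on the birth-variable tests. The section also promises means, SDs or frequencies for all variables, from which a reader given the group sizes could work out intervals. All of that stands, and it keeps the point small. It does not rescue the clause: read as baseline comparability it uses the wrong variables, and read as equivalence it uses the wrong test.

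The sample size also deserves fairness. The T3 visit and chart review are meant to cover every participant, so birth data may exist for more than 40 women per arm. That is why a range is given; the conclusion holds at 58.

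A reader might infer more than the document supports:
- **That the tests will back a perinatal safety claim.** The plan does not say so. Adverse events and maternal and infant health events are collected separately, on their own forms and by record review, although the available text sets out no separate safety analysis.
- **That a treatment effect will be mistaken for baseline imbalance.** The sentence does not call these variables baseline, and their names make the timing plain.
- **That they will enter the models as covariates.** No section proposes this, and they are not among the named confounders.

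**Conclusion.** The clause is wrong as written, on either reading of equivalence. The size of the problem, assuming two-sided 5% tests, equal arms and 40 to 58 women per arm, is a 95% half-width of 0.45 to 0.37 SD and a 74% to 64% chance of missing a true 0.3 SD difference. The percentage-point figures for mode of birth also rest on an assumed cesarean rate; the SD-unit figures do not.

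The consequence is limited to how the birth outcomes are interpreted. It would go too far to conclude that the efficacy analyses are compromised, or that the data will typically be compatible with differences near 0.9 SD. That last figure needs the smaller sample and an observed difference just short of significance. This is a minor point, worth correcting because the correction is nearly free.

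**What to change.** In Descriptive Analyses:
1. Delete the closing clause that gives the birth-variable tests the purpose of assessing equivalence.
2. Move the four variables to a table of post-randomization perinatal outcomes. Report them by arm, with between-group differences and 95% confidence intervals, for all randomized women with a birth record, and state the number in each arm.
3. Judge comparability of the arms descriptively, on T1 variables only.

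If equivalence on any birth outcome is truly intended, state a margin and an interval-based rule in advance, and acknowledge the limited power shown above.

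The cost is an edit to the SAP text and a few added columns in a table. The planned T3 chart review should supply the data, so little or no new collection is needed, and the sample size does not change.
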